An Interactive Response System (IRS) will assign a unique subject identification number at Screening Visit (Visit 1), which will be required for all communication between the Investigator (or designee) and the IRS. Subject numbers will be tracked via the IRS. The IRS will be used to enroll and randomize subjects based on a pre-defined central randomization scheme. An IRS User Guide will describe all steps for enrollment and randomization of subjects.

Subjects meeting all eligibility criteria for selection and inclusion will be randomized to treatment arm 1 (TARM1) or treatment arm 2 (TARM2) in a 1:1 allocation (see Figure 1). Subjects in TARM1 will receive intravitreal GS010 in their first affected eye and their second affected/not yet affected eye. Subjects in TARM2 will receive intravitreal GS010 in their first affected eye and placebo intravitreal injection in their second affected/not yet affected eye. For subjects who report simultaneous onset of vision loss in both eyes, the right or left eye will be selected randomly to serve as the second affected/not yet affected eye. If the right eye is selected randomly as the second affected/not yet affected eye, the left eye will be designated as the first affected eye, and vice versa.

Figure 1: Post-Treatment Follow-up Period 1: up to 2 years post-treatment

Administration of an IOP lowering agent of the investigator's choice will precede all intravitreal injections. Pre-intravitreal injection procedural preparation will include pupil dilation, topical antisepsis, and topical anesthesia. The IMPs (GS010 and placebo) will be administered with a standard intravitreal injection procedure. Each eye will undergo administration of the allocated treatment with a single intravitreal injection, performed as a separate procedure. Please refer to the Intravitreal GS010/Placebo Injection Guide for full details.

Per the Investigator's discretion and according to local standard accepted medical practices, treatment administration to both eyes may be performed at a single Treatment Visit (Visit 3) (i.e. intravitreal injection of both eyes of a given subject is performed the same day as two separate procedures) or may be performed on two consecutive days (i.e. one eye of the subject will be administered the allocated treatment one day and the next day the fellow eye of the subject will be administered the allocated treatment).

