2.2. Secondary objectives

The efficacy objectives listed below will be analyzed for the second-affected/not-yet-affected eyes as the main eye of interest (designated the primary eye). Exploratory efficacy analyses will be conducted for the first affected eyes, but those analyses are secondary to any analysis on the primary eye, which is the second- affected/not-yet-affected eye.

1. To assess the safety and tolerability of bilateral and unilateral intravitreal injection of GS010.
2. To compare the time course of the BCVA LogMAR response in second-affected/not-yet-affected eyes treated with GS010 compared to placebo treatment.
3. To assess, at 1.5, 2, 3, 4 and 5 years post-treatment, the efficacy of intravitreal GS010 compared to placebo intravitreal injection in second-affected/not-yet-affected eyes, by determining the difference in the rate of responder eyes.
4. To compare the time course of the response in second-affected/not-yet-affected eyes treated with GS010 compared to placebo treatment and to estimate the magnitude of the treatment effect at 1.5, 2-, 3-, 4- and 5-years post-treatment, with parameters measured by:
 - a. Spectral-Domain Optical Coherence Tomography (SD-OCT);
 - b. Humphrey Visual Field (HVF)30-2;
 - c. Pelli-Robson Low Vision Contrast Sensitivity (CS).
5. To verify whether a difference exists at 1.5, 2, 3, 4 and 5 years post-treatment, between first affected eyes and second-affected/not-yet-affected eyes treated with GS010, using both an intra-subject and inter-subject analysis, with
 - a. LogMAR BCVA
 - b. Parameters measured by SD-OCT
 - c. Parameters measured by HVF 30-2, and
 - d. Parameters measured with Pelli Robson Low Vision Contrasts Sensitivity.

6. To assess, at 1.5, 2, 3, 4 and 5 years post-treatment, the rate of responders in first affected eyes treated with GS010.
7. To assess humoral and cellular immune responses to Adeno-Associated Virus vector 2 (AAV2) after unilateral and bilateral intravitreal administration.
8. To assess the impact of bilateral intravitreal GS010 administration on Quality of Life (QoL) scales at 1.5, 2-, 3-, 4- and 5-years post-treatment.

3. Study design

GS-LHON-CLIN-05 is a Phase III, global, multicenter, randomized, double-masked for the primary analysis, placebo-controlled, clinical study. As LHON is a neurodegenerative disease, the goal is to administer GS010 as soon as possible upon confirmation of the LHON diagnosis and the causative mutation.

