3.4. Changes to analysis from protocol

1. To address the impact of COVID-19 on study integrity, an extension of the protocol-defined window of time for performing the endpoint has been decided during the data-review before the database lock. Data collected before or after 1.5 year was assessed by the data review committee as relevant and representative of the missing 1.5-year data. Time windows are specified in SAP section 5.3.
2. In the protocol (section 16.4.1.14): In case of missing data up to and including 1.5 years in the primary (second affected/not yet affected) eye, multiple imputation will be used as the primary method of imputation for the following endpoints: BCVA measured in LogMAR, Pelli-Robson CS, and HVF 30-2.

Approach defined in protocol section changed to approach in SAP section 13.1.3: Last observation carried forward method (LOCF) will be used of imputing missing data. In this disease, outside of the very initial phase, BCVA worsen slowly over time (natural history of the disease), whereas active treatment improves BCVA over time, LOCF will therefore tend to favor the placebo eye group and disadvantage the treated eye group.

3. In the protocol (section 16.4.1.12): Sensitivity Analysis: For ITT and mITT analyses, missing data will be imputed using multiple imputations.

Modify by (section 6.4.1.14): Sensitivity analyses of the primary endpoint will be conducted only on observed data (data without imputed values) up to 1.5 years using a MMRM model.

4. Removal of the exploratory analysis coverage (section 16.4.2.4.3) because this analysis is similar to the MMRM model analysis.
5. Removal intra-subject analyses of difference at 1.5, 2, 3, 4 and 5 years post-treatment, between first affected eyes and second-affected/not-yet-affected eyes treated with GS010 (part of objective 5), based on FDA recommendation: "Although use of the contralateral eye to which the GT product is not administered as a control may potentially be considered, it is generally not recommended" Protocol section and analyses described that are not done in SAP:

13.1.6 – Duration of disease is no longer used

13.1.5 – Change of supportive analyses

13.2.3– No more time to event analyses

13.2.3– AUC is no longer done

6. Planned analyses

The following analyses will be performed for this study:

- Analyses for Data Safety Monitoring Board (DSMB) meetings
- Primary efficacy analysis at 1.5 years
- Post-Treatment Follow-Up Period 2 Analyses at 3 and 4 years

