13.1.5. Supportive analysis of primary efficacy variable(s)

Shift table and Mac Nemar test between Eyes on-chart/off-chart for LogMAR BCVA at baseline and Eyes on-chart/off-chart for LogMAR BCVA at 1.5 years by arm will be performed.

The primary analysis with the same model will be repeated for the following:

1. Using the mITT population, if different from the ITT population
2. Using the PP population
3. Same analyses will be conducted on the LogMAR instead of the change of LogMAR (analyses will be not adjusted on LogMAR at baseline but with duration from vision loss)

Using a model at the subject level, with repeated values for eye. We need to have comparison between treatment group (GS010 vs Placebo) and comparison between GS010 eye in GS010/ GS010 ARM and GS010 eye in GS010/ Placebo ARM.SAS code:

ID=identifiant; TREAT =(Placebo in GS010/ Placebo ARM / GS010 in GS010/ Placebo ARM / GS010 first affected eye in GS010/ GS010 ARM / GS010 second affected eye in GS010/ GS010 ARM ; change=Logmar change from baseline; Logmar0=Logmar at baseline;

```
proc mixed data=XXX ;
class ID TREAT (ref="PLACEBO") ;
model change= TREAT logmar0 /s CL;
random intercept/sub=ID type=AR(1);
lsestimate TREAT " GS010 vs Placebo " 1 1 1 -3/cl divisor=3;
lsestimate TREAT " GS010 in GS010/GS010 ARM vs GS010 in GS010/Placebo ARM" -2
1 1 0/cl divisor=2;
run;
```

4. Primary ITT analysis adjusted on potential confusion factors:

ANCOVA will be used to analyze the effect of treatment on the change from baseline of the BCVA, reported in LogMAR at 1.5 years post-treatment adjusted on baseline LogMAR value, and potential confusion factors. A backward selection approach will be considered to keep significant covariates among: Gender, Age at onset of the disease, Duration of vision loss, Pediatrics/Adults, Previous Idebenone treatment, BCVA at baseline as a continuous parameter, BCVA on-chart/off-chart at baseline, BCVA on-chart/off-chart at nadir, LogCS at baseline as a continuous parameter, LogCS on-chart/off-chart at baseline, LogCS on-chart/off-chart at nadir, baseline GCL volume, baseline Quadrant Temporal RNFL, baseline PMB RNFL and Region. We will consider a p-value of <0.2 in univariate model (adjusted on logMAR at baseline) for entry in the multivariate model and a p-value of >0.05 for removal from multivariate model. If a covariable has a p-value>0.05 but

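### In the supportive subject-level model of SAP 13.1.5, both pooled eye contrasts mix treatment with eye order and should give way to the two randomised same-order contrasts

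*SAP*

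**What the plan says.** Protocol 9.1 fixes which eye gets what. In the bilateral arm, "Subjects in TARM1 will receive intravitreal GS010 in their first affected eye and their second affected/not yet affected eye". In the other arm, "Subjects in TARM2 will receive intravitreal GS010 in their first affected eye and placebo intravitreal injection in their second affected/not yet affected eye". No first-affected eye is assigned placebo.

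SAP 13.1.5 includes a supportive subject-level model with repeated values for eye. Its treatment variable has four levels: the placebo eye, the GS010 eye of the GS010/Placebo arm, and two levels for the bilateral arm, "GS010 first affected eye in GS010/ GS010 ARM / GS010 second affected eye in GS010/ GS010 ARM". The fixed part is "model change= TREAT logmar0 /s CL", with a random intercept for subject. Two contrasts are coded:

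- "lsestimate TREAT ' GS010 vs Placebo ' 1 1 1 -3/cl divisor=3";
- one labelled "GS010 in GS010/GS010 ARM vs GS010 in GS010/Placebo ARM", with weights -2 1 1 0 and divisor 2.

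Objective 5 (SAP 2.2) asks whether first- and second-affected GS010 eyes differ, "using both an intra-subject and inter-subject analysis". SAP 3.4 item 5 then announces "Removal intra-subject analyses of difference at 1.5, 2, 3, 4 and 5 years post-treatment" and describes this as part of that objective.

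**The concern.** A contrast labelled as drug against placebo should differ only in drug. Here the GS010 side is two-thirds first-affected eyes and the placebo side has none. Any systematic difference in course between first and second eyes is therefore reported as a drug effect. Only the second-affected GS010 eye of the bilateral arm is a randomised comparator for the placebo eye.

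The companion contrast has the same fault. It sets the average of first and second eyes in the bilateral arm against first eyes only. It is meant to show whether a GS010 eye fares differently when its fellow eye also receives GS010.

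The documents themselves treat eye order as material. Protocol 6.2.1 says that time from onset to treatment may influence the effect, and objective 5 is about the eye-order difference. When SAP 13.2.3 pools both eyes for the responder model, its text lists eye as a factor. The model in 13.1.5 has no such term.

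What is at stake is one supportive estimate. It would carry a smaller standard error than the valid contrast, and so would look the more precise of the two.

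**Working it through.** **Inputs.** SD 0.50 LogMAR after baseline adjustment, 45 per arm, planned effect 0.3 LogMAR, 80% power, two-sided 5% (Protocol 16.2, SAP 3.2). Two inputs are assumptions because the documents give neither: between-eye correlation r = 0.5 (range 0.3 to 0.7) and the eye-order difference d.

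**The plan's own figure.** With an effect of 0.3, SD 0.50 and a two-sided 5% t test, power is 79.5% at 44 per arm and 80.4% at 45. The stated 45 per arm is reproduced.

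**Weights.** Take the levels in the order the code appears to intend: U1 (GS010 first eye, GS010/Placebo arm), B1 (first eye, bilateral arm), B2 (second eye, bilateral arm), P (placebo second eye). The drug indicator is (1, 1, 1, 0) and the first-eye indicator is (1, 1, 0, 0).

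- Contrast 1 = (1, 1, 1, -3)/3. Drug weight = 1/3 + 1/3 + 1/3 = 1. Eye-order weight = 1/3 + 1/3 = 2/3.
- Contrast 2 = (-2, 1, 1, 0)/2. Eye-order weight = -1 + 1/2 = -1/2.
- B2 minus P: drug weight 1, eye-order weight 0.
- B1 minus U1: eye-order weight 1 - 1 = 0.

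Let d be the mean first-minus-second eye difference in LogMAR change that remains after baseline adjustment. Negative d means that first eyes do better. Contrast 1 then estimates the drug effect + (2/3)d, and contrast 2 its intended effect - (1/2)d.

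**Standard errors.** The variance of one level mean is 0.50²/45 = 0.005556. U1 and P come from the same subjects, as do B1 and B2.

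- Contrast 1: variance = 0.005556 × (4/3 - 4r/9). At r = 0.5 this is 0.005556 × 1.111 = 0.00617, so SE = 0.079.
- B2 minus P: variance = 2 × 0.005556 = 0.01111, so SE = 0.105.

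**Bias and null rejection for contrast 1, no drug effect.** Rejection = Φ(-1.96 - b/SE) + 1 - Φ(1.96 - b/SE), with b = (2/3)|d|.

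| assumed \|d\| | bias | rejection, r = 0.5 | r = 0.3 to 0.7 |
|---|---|---|---|
| 0 | 0 | 5% | 5% |
| 0.05 | 0.033 | 7% | 7% |
| 0.10 | 0.067 | 14% | 13–14% |
| 0.20 | 0.133 | 40% | 37–42% |
| 0.30 | 0.200 | 72% | 69–76% |

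A simulation of the four eye groups (20,000 replicates, r = 0.5) gave 13.6%, about 40% and 71.8% at |d| = 0.1, 0.2 and 0.3. B2 minus P stayed at 5% throughout. For contrast 2 the bias at |d| = 0.1 to 0.3 is 0.05 to 0.15 LogMAR, in the opposite direction.

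**Level order.** The three GS010 weights in contrast 1 are equal, so their order does not matter provided placebo is last. Contrast 2 does depend on order, which the SAP never states. If the labels were sorted alphabetically with placebo last, the order would be B1, U1, B2, P. The weight of -2 would then fall on the bilateral first eye, and the line would not estimate what its label says.

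**The case against.** Much of the case on the other side stands.

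- **Status.** The model is supportive, and SAP 6.3 spends all type I error on the primary endpoint. The primary ANCOVA (13.1.4), the covariate-adjusted model (13.1.5 item 4) and the MMRM sensitivity analysis (13.1.6) are coded on second-affected/not-yet-affected eyes. A reader might infer from the rejection rates above that the trial's false-positive rate is inflated. The documents do not support that: the rates belong to a test that carries no alpha.
- **Availability of the valid estimates.** With placebo as reference, the model's printed solution already shows the second-eye GS010 level minus placebo. Repeating the primary analysis in first-affected eyes (SAP 13.3) gives the first-eye comparison between arms. The fault is that neither is the contrast labelled as the result.
- **Baseline adjustment.** It is tempting to argue that second eyes still have to fall and that this alone creates the bias. An eye that has yet to fall has a better baseline LogMAR, and baseline is in the model. In simulations where both eyes share a common follow-up level, raw first-minus-second differences in change of about -0.2 to -0.6 LogMAR left contrast 1 with essentially no bias and rejection of about 5%. Only a residual difference after adjustment matters. Random choice of eye in simultaneous-onset subjects dilutes it further. Neither guarantees d = 0.
- **Direction.** A reader might infer that the contrast favours GS010. It does so only if d is negative; a positive d hides benefit.
- **Objective 5.** A reader might infer that the objective has been abandoned. SAP 3.4 item 5 openly removes only the intra-subject part, and the inter-subject part remains.
- **Contralateral controls.** Contrast 1 does set a subject's GS010 eye partly against the same subject's placebo eye, which sits awkwardly with the advice quoted in SAP 3.4 item 5. That advice is visible only as one sentence, so nothing here rests on it.
- **Pooling.** Protocol 16.4.2.1 lists all GS010 eyes and all placebo eyes as responder groupings. That supports a descriptive summary, not a contrast labelled as a treatment effect.

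**Conclusion.** The point holds as a moderate one about a supportive analysis. The weights are a matter of algebra: as coded, the drug-against-placebo line has an eye-order weight of 2/3 and its companion -1/2 (under the intended level order), and the model contains nothing but baseline LogMAR to offset this. The size cannot be settled from the documents because d is not given. The 0.07 to 0.20 LogMAR bias and 14% to 72% null rejection rest on the assumed |d| of 0.1 to 0.3, 45 per arm, SD 0.50 and a between-eye correlation of 0.5. The primary result stands apart from all of this.

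**What to change.** State the order of the four treatment levels in the SAP, and define each contrast by level name rather than by position. Make the reported treatment contrasts the two randomised same-order ones:

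- (a) the second-affected GS010 eye of the GS010/GS010 arm minus the placebo eye;
- (b) the first-affected GS010 eye of the GS010/GS010 arm minus the GS010 eye of the GS010/Placebo arm.

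Drop the two pooled contrasts. If they have already been reported, keep them, relabel them as non-randomised and confounded with eye order, and show them beside (a) and (b).

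For the inter-subject part of objective 5, add the second-affected GS010 eye of the GS010/GS010 arm minus the first-affected GS010 eye of the GS010/Placebo arm, labelled as a non-randomised eye-order comparison. Comparing the two eyes within the bilateral arm would be intra-subject and would reopen SAP 3.4 item 5.

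Adding an eye-order factor beside the four-level treatment variable does not help, because treatment level already determines eye order.

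The cost is a few lines of code and SAP text, and the loss of the pooled contrast's smaller standard error (0.079 against 0.105 at r = 0.5). That precision belonged to a quantity that mixes drug with eye order.

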#### *16.4.1.8 Primary Model and Test*

The primary analysis is analysis of covariance. The response is the change from baseline at 1.5-years post-treatment. The test will compare the between treatment difference in means adjusted for the LogMAR baseline value and duration of disease, and including the treatment group as a fixed effect.

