3.2. Sample size consideration

Sample size calculation is based on the primary endpoint which is the change from baseline to 1.5 years post-treatment of the visual acuity (LogMAR BCVA). Masked preliminary data of the Phase III RESCUE and REVERSE sham-controlled studies of GS010 and monitored data from the Phase I/IIa safety and tolerability study of GS010 are used to estimate the standard deviation of the change from baseline to each available visit. These data do not take into account a potential treatment effect in the RESCUE and REVERSE studies and if there is an effect, the standard deviation may be overestimated.

From this masked preliminary analysis, a standard deviation of 0.55 LogMAR has been estimated for the LogMAR change from baseline; this is reduced to 0.50 with the inclusion of baseline LogMAR as a covariate. Using this reduced value for Standard Deviation (SD) and a treatment effect of 0.3 LogMAR in the change from baseline, the requested sample size to reach a power of 80% ($\alpha = 0.05$ two-sided) according to a classical Analysis of Covariance (ANCOVA) model including the baseline LogMAR value as covariate has been estimated using SAS PROC POWER to be 45 evaluable subjects per treatment group (i.e. 90 subjects in total). Depending on the number of subjects who terminate early, additional subjects may be enrolled through the end of the recruitment period.

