13.1.4. Primary analysis of primary efficacy variable(s)

The primary analysis will be performed on the ITT population on the planned treatment (as randomized). The primary endpoint is the change from baseline of the BCVA, reported in LogMAR at 1.5 years post-treatment. Descriptive statistics will be presented for the baseline and 1.5 years post-treatment timepoints as well as for the change from baseline to the 1.5 years post-treatment based on data after imputation.

The treatment difference will be assessed with an ANCOVA model which includes terms to adjust for the baseline LogMAR value and includes treatment group as a fixed effect.

The analysis will be performed using a significance level of 0.05 (two-sided).

SAS code:

ARM =subject Treatment arm; change=Logmar change from baseline of second-affected/not-yet-affected eyes; Logmar0=Logmar at baseline

```
proc mixed data=XXX_;
class ARM;
model change=ARM logmar0 /s CL;
estimate " GS010 arm vs Placebo arm" ARM -1 1;
run;
```

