13.3. Other efficacy

Nadir for LogMAR BCVA and for LogCS

Nadir of BCVA/LogCS is defined for each eye of each subject as the worst value observed from baseline to the post-treatment timepoint of interest, including baseline and the post-treatment timepoint values.

For LogCS only, if there is at least one value off-chart between baseline and timepoint, then Nadir cannot be calculated as no off-chart value exists; off-chart LogCS will be imputed a value of 0.

If there are more than one off-chart value from baseline to the timepoint of interest, then the first value over time will be considered the nadir. If there is more than one worst value from baseline to the point of interest (i.e. identical worst values occurring more than once), then the first value over time will be considered the nadir.

The change from Nadir BCVA/LogCS will be calculated for each eye of each subject and will be analyzed as primary endpoint (see section 13.1.4).

The time to Nadir BCVA/LogCS will be calculated for each eye of each subject and will be expressed in Weeks. This analysis will be only descriptive.

Clinically Relevant Recovery (CRR)

At the eye level, a CRR from baseline is defined as:

- For eyes on-chart at baseline, an improvement of at least -0.2 LogMAR
- For eyes off-chart at baseline, eyes which became on-chart.

On-chart value is defined as \leq LogMAR 1.6

Subject with CRR from baseline is defined as subject with a CRR in at least one eye: Subject with at least one eye which was on chart at baseline, and which had an improvement of at least -0.2 LogMAR from baseline, or which was off-chart at baseline but became on-chart.

Subjects with CRR from baseline will be assessed for all subjects, bilaterally GS010 treated subjects and unilaterally GS010 treated subjects.

At the eye level, a CRR from nadir is defined as:

- For eyes on-chart at nadir, an improvement of at least -0.2 LogMAR from nadir
- For eyes off-chart at nadir, eyes which became on-chart.

Subject with CRR from nadir is defined as subject with a CRR in at least one eye: Subject with at least one eye which was on chart at nadir, and which had an improvement of at least -0.2 LogMAR from nadir, or which was off-chart at nadir but became on-chart.

Subjects with CRR from nadir will be assessed for all subjects, bilaterally GS010 treated subjects and unilaterally GS010 treated subjects.

These responder endpoints will be analyzed as section 13.2.3

Other responses parameters

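### SAP 13.1.5: one adjusted ITT model can condition on nadir status, a post-randomization outcome, and another supportive model drops baseline LogMAR

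*SAP*

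**What the plan says.** SAP 13.1.5 item 4 fits an ITT ANCOVA of the 1.5-year change in LogMAR on arm and baseline LogMAR. Further covariates are chosen by backward selection. The candidates include "BCVA on-chart/off-chart at nadir" and on/off-chart LogCS at nadir. SAP 13.3 defines the nadir of each eye as "the worst value observed from baseline to the post-treatment timepoint of interest", with both ends of the interval included.

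The selection rules are:

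- A candidate enters at p<0.2 in a screen adjusted for baseline LogMAR. The screening code has no treatment term.
- It is removed at p>0.05.
- It is kept regardless, as a confounder, if it moves the treatment estimate by 20%.

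Item 3 of the same section repeats the analysis with LogMAR itself as the response: "analyses will be not adjusted on LogMAR at baseline but with duration from vision loss".

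SAP 13.3 adds that change from nadir "will be analyzed as primary endpoint (see section 13.1.4", that is, by the same ANCOVA with a between-arm test.

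The protocol's covariate-adjusted supportive analysis (16.4.1.11) names duration of vision loss at baseline, baseline GCL volume, region and region-by-treatment. It has no nadir term. SAP 3.4 records only that the supportive analyses changed.

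**The concern.** A covariate measured after randomization cannot confound a randomized comparison, but it can carry part of the treatment effect. If GS010 keeps some eyes on the chart, fewer GS010 eyes are off-chart at nadir, and adjusting for that status removes the corresponding part of the effect. The 20% rule makes this worse: for a variable affected by treatment, the movement in the estimate is the bias itself, yet the rule treats it as the reason to keep the variable. The output would still be presented as the primary ITT analysis with adjustment, and a reader would set it against the primary result.

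Item 3 raises a different issue, precision. SAP 3.2 credits baseline LogMAR with reducing the SD of change from 0.55 to 0.50, and item 3 removes that covariate.

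Change from nadir raises a third. Its reference value is itself determined after randomization, so a deeper transient dip in one arm can look like a larger recovery.

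**Working it through.** **Inputs from SAP 3.2 and 13.1.4:** two-sided alpha 0.05, power 80%, "a treatment effect of 0.3 LogMAR in the change from baseline", SD 0.55 unadjusted and 0.50 adjusted for baseline, 45 evaluable per arm. SAP 13.3 puts the on-chart limit at LogMAR 1.6. The documents do not give the baseline SD of LogMAR, the correlation between visits, the course of any effect over time, or the variance explained by duration. These are assumed below.

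**The plan's own figure.** n per arm = 2(1.96+0.842)² × 0.50² / 0.30² = 43.6, so 44 by the normal approximation. With the noncentral t on 2n-3 degrees of freedom, power is 79.5% at 44 and 80.4% at 45. The planned 45 reproduces.

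**Item 4.** The simulation used 4,000 trials per scenario, 45 per arm, seven post-baseline visits and a true effect growing to -0.30 at the last visit. Residual SD of the final change was 0.50. Assumed baseline means were 1.0-1.5, baseline SDs 0.4-0.7 and visit correlations 0.6 or 0.9. LogMAR was kept continuous, without the 2.0/2.3 assignment, and off-chart at nadir meant a worst value above 1.6. Nadir was taken up to 1.5 years, which item 4 does not state.

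| Model | Mean estimate | Power |
|---|---|---|
| Primary ANCOVA | about -0.30 | 79-81% |
| Plus off-chart at nadir | -0.23 to -0.26 | 65-74% |

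- Attenuation is 13-23%. For example, 1 - 0.260/0.300 = 13% and 1 - 0.230/0.298 = 23%.
- One scenario shows the mechanism (baseline mean 1.3, SD 0.5, correlation 0.6). Off-chart at nadir was 60.1% on placebo and 47.0% on GS010, a difference of -0.131. The estimate moved from -0.300 to -0.239. The implied nadir coefficient is 0.061/0.131, or about 0.47 LogMAR, and that coefficient times the arm difference is what the adjustment removes.
- A one-covariate version of the entry, removal and 20% rules kept the nadir term in 80-100% of trials.
- With no effect at any visit, that rule rejected in 4.7-6.0% of trials, against 4.3-6.0% for the primary ANCOVA in the same runs.
- Timing matters. Under other assumed time courses, attenuation was 4-8% for a late effect and 17-26% for an early one. A further set of assumptions (baseline SD 0.5-0.6, correlation 0.8-0.85) reached 38%.
- The direction can reverse. With no lasting effect but an assumed temporary GS010 dip of 0.2-0.3 LogMAR, the nadir-adjusted estimate was -0.05 to -0.12, while the primary ANCOVA stayed at 0.

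**Item 3.** Baseline accounts for sqrt(0.55² - 0.50²) = 0.229 of the SD of change. If change slopes negatively on baseline, the raw 1.5-year LogMAR has SD² = (s0 - 0.229)² + 0.50², where s0 is the baseline SD. A positive slope gives a larger value. SE = SD × sqrt(2/45), and power = Φ(0.3/SE - 1.96).

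| Assumed s0 | SD | SE | Ratio to primary | Power |
|---|---|---|---|---|
| Primary model | 0.500 | 0.105 | 1.00 | 81% |
| 0.3 | 0.505 | 0.107 | 1.01 | 80% |
| 0.5 | 0.569 | 0.120 | 1.14 | 71% |
| 0.7 | 0.687 | 0.145 | 1.37 | 55% |

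These figures precede any gain from duration. To recover the loss, duration would have to explain 1 - 0.25/0.569² = 23% of the 1.5-year variance at s0 = 0.5, or 1 - 0.25/0.687² = 47% at s0 = 0.7. The simulated item 3 estimates, without duration, stayed at about -0.30, so there was no bias.

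**The case against.** The strongest reply is that little depends on these models. SAP 6.3 spends all of the alpha on the primary endpoint, and the rest is secondary, sensitivity, supportive or exploratory. That stands. The primary test is untouched. The mITT and PP repeats, the repeated-eye model and the MMRM all keep baseline LogMAR and have no nadir term. A reader might infer that the checks on the primary result are compromised as a group; they are not.

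It is also fair that the nadir terms are only candidates. For eyes off-chart at baseline, nadir status is fixed by the baseline value. The retention rates come from a simplified rule, not from the full candidate list with its collinearity step. So item 4 may, rather than must, condition on nadir.

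A reader might also infer that no SAP model pairs baseline LogMAR with duration, contrary to Protocol 16.4.1.8 ("adjusted for the LogMAR baseline value and duration of disease"). The documents do not support that in full. Item 4 forces in baseline LogMAR and offers duration of vision loss as a candidate. SAP 3.4 openly drops duration of disease. Protocol 16.4.1.7 lists baseline LogMAR alone, so the protocol is itself inconsistent. Nor is primary-eye duration clearly what 16.4.1.8 means: SAP section 9 ties duration of disease to the first affected eye.

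Finally, one might put a false-positive rate on change from nadir. Protocol 14.2 says that ocular inflammation occurs in most treated subjects, but neither document says that it lowers acuity or by how much. The residual SD of change from nadir is not given either. For an assumed spurious difference of 0.14 at 45 per arm, rejection is Φ(0.14/(0.50 × 0.211) - 1.96), or about 26%, with SD 0.50, but about 82% with SD 0.23. No single rate is supportable. Analysis by the primary model also does not give that test confirmatory status.

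**Conclusion.** The point holds for two supportive models and, as a matter of labelling, for change from nadir.

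- **Item 4** can adjust for an outcome of treatment. If GS010 affects acuity during follow-up, the estimate is biased, usually toward zero: about 13-25% in most assumed scenarios, less if the effect is late and more if it is early. It is not a source of false positives when there is no effect at any visit.
- **Item 3** is unbiased under randomization. Its standard error is about 1.0 to 1.4 times the primary's for an assumed baseline SD of 0.3 to 0.7, before any gain from duration. The loss is close to nil at the low end.
- **Change from nadir** can turn a transient dip into apparent recovery. The size of that artefact rests on assumptions outside the documents.

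That nadir status is a post-randomization variable follows from the SAP's own definition. All of the sizes depend on the assumed baseline distribution, visit correlations and time course.

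**What to change.** 1. Delete both nadir variables from the item 4 candidate list. The list then holds baseline covariates only, including duration of vision loss and region. Region has to stay because SAP 6.1 refers its examination to 13.1.5.
2. Keep baseline LogMAR in item 3, with duration beside it. Given the same covariates, the treatment estimate is then identical to that from the change-score ANCOVA. Separate item 3 from the repeated-eye paragraph and code that follow it, since that code contains baseline LogMAR and appears to belong to the repeated-eye model.
3. In SAP 13.3, label the between-arm test of change from nadir exploratory and interpret it only alongside change from baseline.

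The cost is SAP wording and minor programming. SAP 5.3 refers to visits made after the year 1.5 analyses, so version 10.0 (10 October 2024) appears to follow that unmasking. A change to this version should be documented as made afterwards.
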